## **11. REGULATORY CONSIDERATIONS**

### **11.1 Institutional Review of Protocol**

The protocol, the proposed informed consent and all forms of participant information related to the study (eg, advertisements used to recruit participants) will be reviewed and approved by the Stanford IRB and Stanford Cancer Institute Scientific Review Committee (SRC). Any changes made to the protocol will be submitted as a modification and will be approved by the IRB prior to implementation. The Protocol Director will disseminate the protocol amendment information to all participating investigators.

### **11.2 Data and Safety Monitoring Plan**

Primary internal data monitoring will be performed by the Overall Protocol Director at Stanford and site investigators and their research staff. The Protocol Director will review data to assure the validity of data, as well as the safety of the subjects. The Protocol Director will also monitor the progress of the trial. The Protocol Director will be responsible for maintaining the clinical protocol, reporting adverse event, assuring the consent is obtained and documented, reporting of unexpected outcomes and reporting the status of the trial in the continuing renewal report submitted annually to the IRB and SRC.

A safety monitoring committee (SMC) will be composed of the Protocol Director and research staff, including other site principal investigators. The SMC will conduct regular teleconferences on at least a quarterly basis or more frequent communication between the Protocol Director and research staff may occur via email or teleconference as necessary.

The data will be monitored continuously over the accrual and follow up periods by the investigators and the study coordinators. The Protocol Director will be responsible for maintaining the clinical protocol, reporting adverse event, assuring the consent is obtained and documented, reporting of unexpected outcomes and reporting the status of the trial to the IRB and the Stanford University Cancer Center Data Safety Monitoring Board (DSMB).

### **11.3 Data Management Plan**

The Protocol Director, or his/her designee, will prepare and maintain adequate and accurate participant case histories with observations and data pertinent to the study. Study-specific electronic Case Report Forms (eCRFs) will document treatment outcomes for data analysis. The RedCAP database system will be used and maintained by the PI and/or his designees. The eCRFs will be secured via confidential username and password access to the research team.

## 11.4 Confidentiality

Subjects may be referred to this clinical trial from outside of Stanford. Therefore, study subjects will be assigned a unique study identification (ID) number. Referring physicians will be sent letters by the BMT physicians updating them on their subject's status, including information regarding the expected side effects of the treatment, necessary precautions and also the appropriate follow-up. Specific information regarding the study would not be routinely shared with the referring physician.

Subjects will be assigned a study-specific identification number (a unique number) and their data are entered into a secure database. Access to the database is password-restricted and limited to study personnel.

Research records will be maintained in a secure BMT office, and electronic data will be maintained in a study-specific, secure database. In addition, information from the main Stanford BMT database may be uploaded into the study-specific database.

All study staff will be required to complete HIPAA training. All research staff must complete the IRB human subjects research training. The study subject data are identified by a unique study ID number in the research documents. Access to the research database is limited to approved clinical and research staff. The code is maintained by the Stanford's BMT Database System Administrator, and kept in a secure location.

Study subjects will not be directly identified in any publications, presentations or correspondence.

Private Health Information (PHI) is collected and recorded at the time of the subject's first consultation with the BMT program. Additional information is collected when the subject is enrolled in a clinical trial. PHI may include some or all of the following:

1. Names and initials
2. Telephone numbers
3. Addresses including ZIP code
4. Dates, including date of birth
5. Age; sex; race; and ethnicity
6. Email addresses
7. Identification numbers, including Medical record numbers (MRNs) and Stanford Patient Number (SPN)
8. Relevant medical history as it pertains to their BMT history, malignancy for which they received their BMT, acute and chronic GvHD history, past treatments for GvHD, vital signs, diagnostic test results, laboratory values, physical exam findings, past medical history, including relevant family medical history (eg, coronary heart disease, diabetes, hypertension, etc) that may place them at risk for side effects, medication history/current medications, interval history since last clinic visit, current health complaints, GvHD assessment, and treatment plan.

Other outside agencies that may receive information include:

- Pharmacyclics LLC, its affiliates or collaborators (eg, Janssen Biotech, Inc.) or their representatives

- The Office for Human Research Protections (OHRP) in the US Department of Health and Human Services (DHHS)
- The Food and Drug Administration
- The US Centers for Medicare & Medicaid Services (CMS), the agency responsible for administration of the Medicare program
- Other federal and/or regulatory agencies as required
- Center for International Blood and Marrow Transplant Research (CIBMTR)
- The National Institutes of Health (NIH) / National Cancer Institute (NCI) / National Heart, Lung, and Blood Institute (NHLBI)
- Stanford Data Safety Monitoring Board
- Other Stanford investigators with IRB-approved projects (researchers outside of the BMT program will not have access to subject's identity or personal protected health information (PHI). The data will be managed using a database program. Data sets may be generated to share with investigators outside the program by de-identifying the data).

Samples will be identified by the Subject ID number. Research records are kept in a locked office. Access to the office is limited to key access. Only study personnel within the research program have access to the electronic database, the research records, or the code linking the samples to subject's identifying information.

## **11.5 Reporting Mechanisms**

The study Protocol Director (or designee) will be responsible for the coordination and development of all protocol amendments. Any changes to the protocol or consent will be made in the form of an eProtocol modification, and will be approved prior to implementation. Any amendments to the Protocol or Informed Consent Form protocol must be sent to Pharmacyclics for review and approval prior to submission to the IRB. This process will be included in the monitoring plan. Changes or amendments to the protocol or consent will be reported to the IRB, FDA and NHLBI. All IRB actions will be reported to the DSMC, NHLBI and FDA.

## **12. STATISTICAL CONSIDERATIONS**

### **12.1 Statistical Design, Effect Size, and Sample Size**

This study is designed as a single-arm efficacy trial using historical published controls. This study's primary endpoint is the incidence of relapse at 18 months after allogeneic HCT for AML/ALL. Baseline relapse rates after reduced-intensity conditioning for these diseases in the published literature vary from 40–60% (1-6). For the purposes of study design, we will use a relatively conservative baseline relapse risk of 45%. This study is designed to detect a decrease in relapse rate from 45% to 25%. Therefore, in the power analysis we will assume that the true relapse rate in the study population is 25%, while the null hypothesis holds that the relapse rate is 45%. Under these conditions, using intent-to-treat analysis, a sample size of 50 enrolled subjects will provide 84% power to conclude that the relapse rate is lower than 45% at the two-sided significance level of 0.05. Conservatively assuming that 45 of these 50 subjects meet the secondary criteria to continue to ibrutinib treatment (Appendix B) and are treated with ibrutinib, a subgroup analysis restricted to these 45 subjects will have 78% power to conclude that the relapse rate is < 45% with a significance level of 0.05.

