## 1. OBJECTIVES

### 1.1 Primary Objective

- To reduce the incidence of relapse at 18 months after RIC and allogeneic HCT for AML, ALL, and CML in blast crisis from a historical baseline of 45% to 25%, using ibrutinib maintenance therapy.

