#### **10.1.1 Relevant Subsets**

The primary and secondary outcomes will be measured on all enrolled subjects.

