### **12.3 Analysis Population**

Subjects who are enrolled but never treated with ibrutinib (eg, due to failure to meet the secondary criteria to continue to ibrutinib treatment) will be included in the primary analysis, which will be performed as an intention-to-treat analysis. However, they will not be counted toward the overall accrual goal of 45 subjects. A planned subset analysis will be performed testing the primary and secondary endpoints in the subset of subjects who receive at least 1 dose of ibrutinib on study.

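### The plan gives three incompatible sample-size statements, so the intention-to-treat denominator is not fixed, and its two powers assume 25% relapse in subjects who never receive ibrutinib as well

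*Combined protocol and SAP*

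**What the plan says.** **Power.** Section 12.1 takes a null of 45% and says that "in the power analysis we will assume that the true relapse rate in the study population is 25"%. On that basis "a sample size of 50 enrolled subjects will provide 84% power to conclude that the relapse rate is lower than 45"% at two-sided 0.05, analysed by intention to treat. It then assumes that 45 of the 50 go on to ibrutinib and says that "a subgroup analysis restricted to these 45 subjects will have 78% power to conclude that the relapse rate is < 45"%. Baseline relapse rates "in the published literature vary from 40–60"%, from which 45% is chosen. The primary objective (1.1) is a reduction "from a historical baseline of 45% to 25%, using ibrutinib maintenance therapy".

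**Who is analysed.** Section 10.1.1: "The primary and secondary outcomes will be measured on all enrolled subjects". Section 12.3 says that subjects enrolled but never treated "will be included in the primary analysis, which will be performed as an intention-to-treat analysis", but also that "they will not be counted toward the overall accrual goal of 45 subjects". It plans tests of the primary and secondary endpoints in those who take at least one dose.

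**How many.** The sample-size row of the synopsis has 50 subjects who are both enrolled and treated. Its statistical row has 50 screened and enrolled, with 84% power. Section 12.1 has 50 enrolled, 45 of them treated. Section 12.3 has a goal of 45 that leaves out the never-treated.

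**Who is treated.** Under 3.1.2, 3.2.2 and Section 4, ibrutinib can start only between Day +60 and Day +90, and relapse since transplant is a bar. So are inadequate blood counts or organ function, second-line therapy for acute GvHD, and uncontrolled infection.

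**The concern.** The three accrual statements cannot all hold if anyone goes untreated. Under 12.3 enrolment continues until 45 are treated, every untreated subject enrolled on the way enters the primary analysis, and the total has no stated limit. The cutoff for the primary test and its power depend on that total.

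The two powers raise a related question. If 25% holds both in all 50 and in the 45 treated, it also holds in the other 5. Those 5 get no drug, and the drug is the stated means of moving from 45% to 25%. A reader who takes 84% as the chance of success when ibrutinib brings relapse to 25% is relying on an assumption about subjects who never take it.

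The treated-only test has its own problem. Its subjects have already survived two to three months without relapse, while the 45% null counts relapses from the day of transplant.

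**Working it through.** **Inputs.** Null 45%, alternative 25%, two-sided 0.05, 50 enrolled, 45 treated, 5 untreated (all from 12.1). Untreated rates other than 25% are assumptions; 45% and 40–60% are the plan's baseline and its published range.

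**1. Reproduce the plan's figures.** Exact binomial test, rejecting at the largest count whose lower tail under 45% is at most 0.025.
- n = 50: reject at 15 or fewer. P(X ≤ 15 | 50, 0.45) = 0.0220; power P(X ≤ 15 | 50, 0.25) = 0.8369, or 84%.
- n = 45: reject at 13 or fewer. P(X ≤ 13 | 45, 0.45) = 0.0201; power P(X ≤ 13 | 45, 0.25) = 0.7841, or 78%.

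Both match. Section 12.1 does not repeat the sidedness for the subset; 78% reproduces with a two-sided 0.05 test (one-sided 0.05 would give 86.7%).

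**2. Implied rate in the untreated.** (50 × 0.25 − 45 × 0.25) / 5 = 1.25 / 5 = 25%.

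**3. If 25% is the rate on ibrutinib.** Total relapses are Bin(45, 0.25) + Bin(5, q), with the cutoff kept at 15 of 50.

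| Untreated rate q | Overall rate | ITT power |
|---|---|---|
| 20% | 24.5% | 86% |
| 25% | 25.0% | 84% |
| 40% | 26.5% | 77% |
| 45% | 27.0% | 74% |
| 60% | 28.5% | 66% |
| 100% | 32.5% | 41% |

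Power equals 80% at q of about 33.5%.

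**4. If 25% is the rate in all 50.** ITT power stays at 84%. The treated rate is (12.5 − 5q) / 45. At q = 45% it is 10.25 / 45 = 22.8%, and P(X ≤ 13 | 45, 0.228) = 87%, not 78%. Over q = 40% to 60%, treated-only power is 85% to 92%.

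**5. Treated-only null.** Suppose 45% of all 50 relapse (22.5) and r of those are among the 5 untreated. The treated null rate is then (22.5 − r) / 45, and the real lower-tail error of the 13-of-45 rule is:

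| r | Treated null rate | Error |
|---|---|---|
| 0 | 50.0% | 0.3% |
| 1 | 47.8% | 0.8% |
| 2 | 45.6% | 1.7% |
| 3 | 43.3% | 3.4% |
| 4 | 41.1% | 6.3% |
| 5 | 38.9% | 10.9% |

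If the untreated relapse at exactly 45% (r = 2.25), the treated null is 20.25 / 45 = 45.0% and the error is 2.0%.

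**6. Accrual readings.** The cutoff is reset for each N. The untreated counts beyond 5 of 50 are illustrative.

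| Treated + untreated | N | Cutoff | Power, 25% in all | Power, 25% on drug and 45% untreated |
|---|---|---|---|---|
| 45 + 5 | 50 | 15 | 84% | 74% |
| 45 + 8 | 53 | 16 | 85% | 70% |
| 45 + 12 | 57 | 17 | 84% | 61% |
| 50 + 5 | 55 | 17 | 88% | 80% |
| 50 + 6 | 56 | 17 | 86% | 76% |

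Part of the movement between rows is the stepwise cutoff of an exact test, as the last two rows show.

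**The case against.** A reader might infer that 84% or 78% is miscalculated, or that the plan hides its assumption. Neither is supported. Both powers reproduce, and 12.1 states 25% for the study population in the same place as it specifies intention to treat, which includes the untreated. Computing power for 50 and for 45 at one planning value is ordinary practice. What is missing is a separate rate for the untreated, or a sentence saying that 25% is meant to cover them.

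It is also tempting to say that the true power is 74%. The documents do not support that either. The 45% is a literature baseline for reduced-intensity transplants in general, not for patients who fail the criteria at Day +60 to +90. Some of these will have relapsed already; others may die early without relapse or be barred for unrelated reasons. Their rate could lie on either side of 45%, and power stays at 80% or more up to about 33.5%. The objective in 1.1 can be read as describing the whole transplanted population under a maintenance strategy, in which case 84% stands.

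Nor do the documents show that the treated-only test is anti-conservative. Its error exceeds 2.5% only if at least 3 of the 5 untreated relapse, and it is conservative if few do. The mismatch of time origin and selection stands; its direction is open.

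Finally, with 25% in everyone, each accrual reading tabulated above leaves power at 84% or higher. The accrual conflict matters because the denominator is unfixed, and not because the literal assumption fails.

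**Conclusion.** This is a point of consistency and of design assumption, minor to moderate in weight. There is no arithmetic error.

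The accrual conflict is certain from the text and leaves the size of the primary analysis set open. With the untreated at the plan's 45% baseline, one of the two printed powers changes whichever way 25% is read: 84% becomes 74% (77% to 66% over the 40–60% range) if it is the on-drug rate, or 78% becomes about 87% if it is the overall rate. These are sensitivity figures, conditional on 5 untreated of 50 and on an untreated rate that the documents do not give. The treated-only comparison is not like for like, with an error between 0.3% and 10.9% depending on outcomes in 5 people.

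The primary intention-to-treat test, its 45% null and its 2.2% lower-tail error at N = 50 stand.

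**What to change.** 1. Put one accrual rule in the synopsis, 12.1 and 12.3, either a fixed number enrolled or a fixed number treated plus an expected untreated share. Let it fix the intention-to-treat denominator, and compute the cutoff and power for it.
2. In 12.1 and the synopsis, state the relapse rates assumed for treated and untreated subjects and restate the power: for example, 74% with 25% on ibrutinib and 45% in 5 untreated of 50. Alternatively, keep 84%, say that it assumes 25% in untreated subjects too, and give 74% as a sensitivity figure.
3. Report the treated subset as supportive: cumulative incidence of relapse from ibrutinib start, or from a landmark in the Day +60 to +90 window, with a 95% confidence interval. Drop the 78% power claim against the from-transplant 45%.

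The cost is wording and recalculation, with no extra patients unless the sponsor chooses a larger target. The stated power may look less favourable, and the subset yields an estimate in place of a test. Keeping a subset test would require a null for patients relapse-free at the landmark, and so landmark data from comparable patients not given ibrutinib, which the documents do not contain.

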EXCLUSION CRITERIA	
 
Active involvement of the central nervous system with malignancy (previous CNS involvement is allowed if clearance of CNS disease has been documented prior to enrollment)
 
Pregnant or breastfeeding
 
Karnofsky Performance Status < 60%
 
Active leukemia (> 5% leukemic blasts in peripheral blood or bone marrow)
 
Non-hematologic malignancy with a life expectancy of < 5 years
 
Known history of human immunodeficiency virus (HIV) or active hepatitis C virus (HCV) or hepatitis B virus (HBV) infection. Subjects who are positive for hepatitis B core antibody or hepatitis B surface antigen must have a negative polymerase chain reaction (PCR) result before enrollment. Those who are PCR-positive will be excluded.
 
Known bleeding disorders (eg, von Willebrand's disease) or hemophilia.
 
History of other malignancies, except: 
 
Malignancy treated with curative intent and with no known active disease present for <math>\geq</math> 3 years before the first dose of study drug and felt to be at low risk for recurrence by treating physician.
 
Adequately treated non-melanoma skin cancer or lentigo maligna without evidence of disease.
 
Adequately treated carcinoma in situ without evidence of disease.
 
 
 

TREATMENT SUMMARY	Subjects will be treated with ibrutinib 420 mg orally once daily, starting between Day +60 and Day +90 after allogeneic HCT and continuing until 18 months post-transplant
SAMPLE SIZE	50 subjects enrolled and treated
STATISTICAL CONSIDERATIONS	Screening and enrollment of 50 subjects will provide 84% power to detect a decrease in the incidence of relapse at 18 months post-transplant from 45% to 25%

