#### **4.2 Criteria for Removal from Study**

Ibrutinib will be continued until 18 months post-transplant, or until one of the following occurs: disease relapse; or discontinuation due to adverse events. Subjects with leukemia relapse after allogeneic HCT will discontinue the study drug, and may be treated with any and all appropriate therapies, including investigational agents, at the discretion of the treating physician.

Subjects will be withdrawn from study treatment if one of the following occurs: leukemia relapse; unacceptable toxicity requiring interruption of ibrutinib for more than 28 continuous days; investigator decision; withdrawal of consent by the subject for further treatment and/or follow-up; pregnancy; or study termination. All enrolled subjects, regardless of discontinuation of study treatment, will be followed for leukemia relapse and survival until 18 months after allogeneic HCT unless the subject withdraws consent for follow-up.

Withdrawal from the study will occur under the following conditions: withdrawal of consent for follow-up observation by the subject; loss to follow-up; study termination; or death. When an enrolled subject withdraws from the study, the reason for withdrawal should be documented, as should the subject's willingness to participate in follow-up visits or assessments.

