## 12.2 Interim analyses

We will monitor major adverse event rates as described above, in particular serious bleeding complications (hemorrhage Grade 3 or 4, as defined by CTCAE v4.0). We will monitor and estimate the incidence rate of serious bleeding in study participants, and report all occurrences and corresponding analytic summaries (such as the estimated incidence rate with 95% confidence intervals) to the DSMB to assist in decision-making regarding early termination for safety.

Allogeneic HCT is an intensive therapy with many associated side effects and toxicities related to the transplant conditioning regimen; the ensuing immunosuppressed status; adverse effects of standard post-transplant medications; and graft-vs-host interactions or GvHD. Toxicities, including Grade 4 toxicities, are relatively common. Non-relapse mortality (NRM) is a definitive endpoint which captures fatal effects of any aspect of the transplant process outside of disease relapse, and thus represents the most accurate and reproducible measure of the toxicity and safety of the allogeneic HCT process.

The baseline cumulative incidence of NRM after allogeneic HCT for acute leukemia with FLU/MEL conditioning was estimated in a recent large cohort study at 20% (22). In order to ensure that patients are not harmed by the study intervention, the formal stopping rule below monitors that the study intervention does not increase the risk of NRM in participants.

The stopping rule is based on the incidence of NRM at 1 year after allogeneic HCT. Patients will be evaluable with regard to the stopping rule if they die or if they reach 1 year post-transplant, whichever occurs first. The stopping rule will be tested every increment of 5 evaluable patients. The stopping rule will be triggered if any of the following conditions are met:

Number of evaluable patients	Number of patients with NRM
5	3
10	5
15	6
20	8
25	9
30	10
35	12
40	13

If the stopping rule is triggered, the study will be terminated, and FDA so notified. This stopping rule provides 80% power to detect an increase in NRM with a type I error rate of 0.05. The stopping rule was constructed using the Pocock boundary with the same significance level for all looks at the data. The rule was created using R v.3.1.3 and the clinfun package.

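### The 84% power is that of a 50-subject test that always completes, and 4.2 and 12.2 leave open whether a mandatory non-relapse mortality (NRM) stop ends the follow-up it needs

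*Combined protocol and SAP*

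**What the plan says.** - **Power (12.1).** Under the null, "the null hypothesis holds that the relapse rate is 45" percent; for power, "we will assume that the true relapse rate in the study population is 25" percent. The test is "at the two-sided significance level of 0.05", by intention to treat. The claim is that "a sample size of 50 enrolled subjects will provide 84% power to conclude that the relapse rate is lower than 45" percent. For 45 treated subjects, "a subgroup analysis restricted to these 45 subjects will have 78% power". The synopsis repeats the main claim: "Screening and enrollment of 50 subjects will provide 84% power to detect a decrease in the incidence of relapse at 18 months post-transplant". Neither place mentions early termination.
- **NRM rule (12.2).** Looks are tabulated at 5, 10, 15, 20, 25, 30, 35 and 40 evaluable patients, with counts 3, 5, 6, 8, 9, 10, 12 and 13. The baseline NRM is 20% and the rule's stated type I error is 0.05. A patient is evaluable on death or on reaching 1 year post-transplant. The consequence is mandatory: "If the stopping rule is triggered, the study will be terminated, and FDA so notified". Bleeding data, by contrast, go to the DSMB to inform a decision.
- **Follow-up (4.2).** One paragraph promises all enrolled subjects relapse and survival follow-up to 18 months regardless of treatment discontinuation, unless consent for follow-up is withdrawn. The next opens: "Withdrawal from the study will occur under the following conditions: withdrawal of consent for follow-up observation by the subject; loss to follow-up; study termination; or", and the last item on that list is death.
- **Accrual (3.4 and 12.4).** About 1 year.

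**The concern.** The power figure needs the 18-month relapse status of 50 subjects. The NRM rule can end the study before that status is known, and the plan expects 20% NRM even when ibrutinib does no harm. If termination also ends follow-up, an effective and harmless drug has a real chance of never reaching its primary analysis, and the printed 84% makes no allowance for this. Little would be gained in exchange: with 1-year accrual most subjects are already enrolled when a boundary is typically crossed, so ending follow-up discards primary-endpoint data while preventing little further enrolment.

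**Working it through.** **1. Reproduce the plan's figure.** Inputs from 12.1: null 45%, alternative 25%, two-sided 0.05 (0.025 in the lower tail), N = 50.
- Largest c with P(X ≤ c | 50, 0.45) ≤ 0.025: c = 15, tail 0.0220.
- Power = P(X ≤ 15 | 50, 0.25) = 0.8369, the stated 84%.
- For N = 45: c = 13, tail 0.0201, power 0.7841, the stated 78%.

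Both are single-look figures with no stopping.

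**2. Add the NRM rule, assuming a stop ends the primary analysis.** Each subject has NRM by 1 year (0.20, from 12.2), relapse by 18 months (0.25, from 12.1) or neither (0.55), independently of other subjects. Looks are taken in transplant order. With k NRM events and r relapses after i subjects:

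P_i(k, r) = 0.20·P_{i−1}(k−1, r) + 0.25·P_{i−1}(k, r−1) + 0.55·P_{i−1}(k, r)

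At i = 5, 10, …, 40, paths at or beyond the boundary are removed as stopped. Net power is the sum of P_50(k, r) over r ≤ 15.

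| NRM | Count reached: stopped | Count reached: net power | Count exceeded: stopped | Count exceeded: net power |
|---|---|---|---|---|
| 10% | 1.1% | 82.7% | 0.1% | 83.6% |
| 15% | 4.8% | 79.4% | 0.9% | 82.8% |
| 20% | 14.8% | 70.3% | 5.1% | 78.9% |
| 25% | 33.7% | 53.2% | 17.4% | 67.5% |

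Taking the stated 0.05 at face value: 0.8369 × 0.95 = 0.795.

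**3. Split the gap at 20% NRM.** The total on the count-reached reading is 83.7 − 70.3 = 13.4 points. Of this, 83.7 − 78.9 = 4.8 points remain when the false-stop rate is about 5%. The other 78.9 − 70.3 = 8.6 points arise because the table, read as counts reached, stops 14.8% of trials and not 5%. The first look alone gives P(X ≥ 3 | 5, 0.20) = 0.058.

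**4. Check the order of looks.** In 12.2 deaths count at once and survivors only at 1 year, so early looks are enriched for deaths. Simulations assumed uniform entry over 12 months, NRM times uniform over the first year and 20% NRM. If none of the relapsing subjects die within the year, about 94% of trials stop on the count-reached reading and about 82% on the count-exceeded reading. If 40% of them do, the figures are about 90% and 71%. The exact values depend on these timing assumptions; the direction does not.

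**5. Keep follow-up and the intention-to-treat test after a stop.** In transplant order with 12-month accrual, about 99.9% of stopped trials already have all 50 enrolled, and simulated power is about 84% on either reading. In calendar order the median enrolled at the stop was 46 to 48. The same exact test then gives P(X ≤ 13 | 46, 0.25) = 0.757 (null tail 0.0151) and P(X ≤ 14 | 48, 0.25) = 0.800 (null tail 0.0184). So 84% is recovered only if essentially all 50 are enrolled.

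**The case against.** The strongest objection is that 4.2 does not clearly end follow-up. Study termination also appears there among the reasons for leaving study treatment, and the promise of 18-month follow-up comes directly after that list, with withdrawal of consent for follow-up as its only exception. The paragraph on withdrawal from the study then asks for the subject's willingness to take part in later assessments to be recorded. On that reading the loss largely disappears (step 5). This stands, and it is why the loss is stated conditionally. It does not settle the matter, because the following paragraph puts study termination beside loss to follow-up and death, and 12.2 does not say what happens to outcome data after a stop.

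A reader might also infer that 84% is miscalculated, or that the trial's power is simply 70%. The documents support neither. The 84% reproduces exactly, and quoting efficacy power apart from a safety rule is common. The 70% requires three things together: termination ends follow-up, reaching the count is enough, and NRM is 20%. Most of that drop reflects a separate mismatch between the NRM table and its stated 0.05.

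Finally, 20% is the upper of the plan's reduced-intensity figures: section 7.2 gives about 10% for sibling and 20% for unrelated donors, and 12.2 ties its 20% to one of the two permitted conditioning regimens. That is fair, and at 10% NRM in transplant order the loss is at most about 1 point. But 20% is the baseline on which the rule is built, and unrelated donors are eligible.

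**Conclusion.** The point holds as a conditional one. The 84% is correct for a 50-subject, single-look test that completes. The plan does not say whether an NRM stop leaves that test possible, and 4.2 can be read both ways. If a stop ends follow-up, power at 25% relapse and 20% NRM is about 79% (stated 5% false-stop rate, or count exceeded) or about 70% (count reached). At 10% to 15% NRM it is about 79% to 84% across the two readings.

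These figures rest on independent subjects and looks in transplant order. They are not worst cases: under the evaluability rule as written with 1-year accrual, stopping would be far more frequent, so neither 70% nor 79% should be presented as the power of the design as written. If follow-up and the primary analysis survive a stop, the loss largely goes away, provided essentially all 50 subjects are enrolled by then.

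**What to change.** **Primary change.** Reconcile 4.2 and 12.2. State that crossing the NRM boundary does not end outcome follow-up, that subjects already enrolled are followed for relapse and survival to 18 months, and that the primary intention-to-treat analysis, with its confidence interval, is reported on them. Remove study termination from the conditions that end this follow-up. In 12.1 and the synopsis, label 84% as the power with all 50 subjects enrolled and followed. The boundary and what it means for treatment are not touched by this change.

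**Only if termination is meant to end follow-up.** Label 84% in 12.1 and the synopsis as the fixed-sample figure, conditional on completion. Print beside it the power net of the NRM rule, computed under the trigger reading and evaluability rule actually intended, at 10%, 15% and 20% NRM. This is an alternative to the primary change and should not be combined with it: once follow-up is kept, the net figures no longer describe the design.

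**Separate item for 12.2.** Reconcile the NRM table with its stated 0.05 type I error, and say whether the listed count must be reached or exceeded.

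**Cost.** Wording in four places, and a recalculation if the second route is taken. The stated power may become less favourable. No extra patients or procedures are needed, since 18-month follow-up is already planned for all enrolled subjects.
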